Cincinnati Children's	Cyanotic patients at baseline: Initiate bypass at 21% FiO2 and then increase to 200-250. Decrease to 80-120 prior to cross clamp removal and then goal of 200-250				
	All other patients: Maintain >200, decrease to 80-120 just prior to cross clamp removal and then 200-250 afterwards				

ANSWER CHOICES	RESPONSES
Match patient's baseline	0.00%
< 30	0.00% 0
30 - 70	0.00% 0
71 - 120	15.38% 6
121 - 200	30.77% 12
201 - 300	43.59% 17
301 - 400	2.56% 1
> 400	7.69% 3
TOTAL	39

Figure 1: Survey Data results of NPC-QIC Perfusion Practices: Goal PaO2 while on cardiopulmonary bypass.

Specific Aims:

To assess oxidative stress and end organ injury in the normoxia versus supra-physiologic oxygen groups.
 Hypothesis 1a: Normoxia will be associated with reduced oxidative stress as measured by
 thiobarbituric acid reactive substances (TBARS), a marker of lipid peroxidation. We also anticipate
 reductions in other measures including protein carbonyl, 8-isoprostane, and whole blood reduction oxidation potential.

Hypothesis 1b: End organ injury will be reduced as assessed by biomarkers of renal (Neutrophil gelatinase-associated lipocalin), neurologic (Glial fibrillary acidic protein, Tau), liver (Intestinal fatty-acid binding protein), vascular (Angiopoietin 2), and myocardial injury (Troponin I) as well as immune system activation (IL-6, IL-10).

- To evaluate the safety profile of a strategy of normoxia versus supra-physiologic oxygen.
 Hypothesis: Observed major adverse events including in-hospital mortality, cardiac arrest, need for mechanical circulatory support, seizures, and dialysis will be similar or lower in the normoxia group.
- 3. To investigate optimal endpoints in the study of the clinical impact of normoxia.

We will assess clinical endpoints that may be reflective of a reduction in oxidative stress to understand effect sizes and inform the design of subsequent trials. These endpoints will include post-operative length of stay, days alive and out of the intensive care unit (ICU) at 30 days after surgery, a composite

outcome of major adverse events as described above, and a global rank score.

Study Design:

Participants:

Single center (University of Michigan) randomized pilot study in infants less than 30 days of age

undergoing heart surgery with cardiopulmonary bypass. The trial will be unblinded with respect to

knowledge of treatment assignment as the majority of clinical personnel will have knowledge of the

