cardiopulmonary bypass strategy based on blood gases and operative documents.

Inclusion Criteria:

• Age less than 30 days of age at time of surgery with need for cardiopulmonary bypass with

cardioplegic arrest (with or without deep hypothermic circulatory arrest)

• Diagnosis with cyanosis at baseline (pre-operative PaO2 of less than 50mmHG) due to:

o Complete admixture lesion (example: hypoplastic left heart syndrome, total anomalous

pulmonary venous return, truncus arteriosus, pulmonary atresia with VSD)

o Transposition physiology (example: D-Transposition of the great arteries or Double

outlet right ventricle with subpulmonary VSD)

o Right-to-left shunt (example: Tetralogy of Fallot, double outlet right ventricle with

suboaortic VSD and pulmonary stenosis)

Exclusion Criteria:

• Corrected gestation at time of surgery less than 37 weeks

• Prior cardiac arrest

• Current or prior history of ECMO support

• Current or prior history of needing renal replacement therapy with dialysis

• Prior cardiac surgery requiring cardiopulmonary bypass

• Diagnosis of Ebstein's Anomaly

• Known genetic syndrome other than Trisomy 21 or DiGeorge Syndrome

ProtocolVersion: 1.4 Date: 03122021

7

Subject Availability:

Based on historical data, the number of patients that fit the inclusion criteria would be about 40-50 patients

per year in this single center study. A sample size of 21 patients per treatment group (42 total patients) will

be enrolled. With a 50-67% consent rate, the study duration will be approximately 24 months.

Trial Enrollment and Randomization:

Infants will be randomized into two groups:

1. Normoxia Group (with controlled re-oxygenation):

a. Goal PaO2 on cardiopulmonary bypass of 60-100 mm Hg using lower FiO2 (blended

sweep gas) via oxygenator

b. Post-bypass, goal of PaO2 < 100 mm Hg by anesthesia and in ICU via oxygen titration via

mechanical ventilator for 24 hours post-op.

2. Standard of Care Group: Current standard of care

Randomization will be performed in random permuted block sizes of 2 or 4 and stratified by "Stage I

Palliation" (Norwood arch reconstruction with shunt placement [Right ventricle-to-pulmonary artery shunt,

modified Blalock-Taussig shunt, or central aortopulmonary shunt]) in each treatment group. Patients

undergoing Stage I palliation are known to have higher rates of complications and mortality at baseline and

therefore the stratification will be done to control for this in the randomization.

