Study Protocol:

Please see Figure 2 for a summary of the study protocol.

1. Preoperative:

Patients that meet the defined inclusion and exclusion criteria will be identified and the families will be

8

approached for consent prior to the scheduled surgery.

Patients that are enrolled in the study will have the following pre-operative studies:

ProtocolVersion: 1.4

Date: 03122021

• Head ultrasound (not currently standard of care but will be used to evaluate for any brain injury

in each group)

• Renal function and liver function panel (within 24 hours prior to surgery)

2. Operating Room:

Patients will be brought to the operating room in a standard fashion. Anesthesia will induce general

anesthesia per protocol and secure an airway (if needed) and place invasive lines. Patients will have labs

drawn (baseline biomarkers of oxidative stress, troponin level, and Redox potential) and an arterial blood

gas.

All patients will have a median sternotomy and be cannulated onto cardiopulmonary bypass via standard

procedures at the discretion of the surgery team.

3. Initiation of Cardiopulmonary Bypass:

The cardiopulmonary bypass circuits will be set up and primed per standard institutional protocols.

"Normoxia" Group: Prior to cannulation, a blood gas will be drawn from the cardiopulmonary bypass

circuit and correlated to the CDI (in-line PaO2 monitor). The FiO2 of the oxygenator will then be titrated

to achieve a PaO₂ of the circuit and CDI of 60-100 mm Hg. After cannulation, frequent blood gases will

be checked per protocol and correlated with the CDI to maintain a PaO₂ of 60-100 mm Hg.

"Standard of Care" Group: After cannulation, frequent blood gases will be checked per protocol on bypass

and correlated with the CDI to maintain a PaO₂ of 200-300 per standard practice.

4. Weaning of Cardiopulmonary Bypass:

At the end of re-warming, a blood sample will be obtained for appropriate studies.

"Normoxia" Group: As cardiopulmonary bypass is being weaned, anesthesia will initiate mechanical

ventilation with an FiO2 of 50% or less (unless clinically necessary) to achieve oxygen saturation and PaO2

9

goals that fit within the expected range for the patient's physiology:

1. Single ventricle patients (PaO₂:35-45 and oxygen saturation 75%-85%)

2. Two ventricle patients (PaO₂: 60-100 and oxygen saturation >92%)

ProtocolVersion: 1.4

. . .

Measures of oxygen delivery such as NIRS monitoring, mixed venous oxygen saturations, and

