lactate measurements will be used to verify appropriate oxygen delivery.

"Standard of Care" Group: As cardiopulmonary bypass is being weaned, anesthesia will initiate mechanical

ventilation per standard protocols. Ventilation will be continued in the ICU and adjusted per standard goals

per the intensivist.

5. Post-Operative Course:

After transfer to the PCTU from the OR, the goals as stated above based on the patient's physiology will

be maintained for 24 hours after the surgery per the goals per group and physiology.

After cardiac surgery, the following tests and evaluation will be performed:

1. At 2, 6, and 24 hours after surgery (time marked as decannulation from cardiopulmonary

biomarkers for oxidative stress, inflammation, vascular injury, neurologic,

myocardial, and renal injury will be drawn.

2. At 24, 48, and 72 hours after surgery: renal function and liver function panels will be obtained

3. A head ultrasound will be performed at 24 and 72 hours after surgery

4. EEG monitoring may be connected to each infant after arrival to the ICU as part of the standard

of care.

6. Adverse Event Assessment

Assessment of Serious Adverse Events will be performed 1month post surgery. A chart review will be

performed by the study team. If a chart review can't be accomplished, the study team will contact the patient

[figure not shown]
via phone call for an assessment. See Serious Adverse Event section of the protocol for specific definitions.

10

Date: 03122021

ProtocolVersion: 1.4

Figure 2: Study protocol flow chart

Outcomes and Analysis:

Analysis will be performed on the basis of the intent-to-treat principle. Baseline characteristics will be compared between the treatment groups using standard univariate tests.

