2. Days alive and out of the ICU or hospital at 30 days after surgery: This endpoint has been used to measure

outcomes in other adult trials and a limited number of pediatric trials. It can incorporate both mortality and

various morbidities that may be influenced by strategies to reduce oxidative stress as most significant

complications or end-organ injury can extend stay in the ICU or hospital. As a continuous variable, it is

also statistically expedient allowing for smaller sample sizes to detect significant differences in treatment

groups.

3. Composite outcome: A composite endpoint can combine multiple relevant morbidities or adverse events

such as those described above. Disadvantages are that all are inherently assumed to be of equal severity.

12

ProtocolVersion: 1.4

Date: 03122021

4. Global rank score: The rank score has the advantage of allowing for the combination of various endpoints

into a single quantifiable endpoint like a composite outcome, however also allows weighting of the severity

of the component endpoints, as opposed to a traditional composite endpoint where all endpoints are treated

equally. It has been utilized increasingly in other trial settings. In this study, scores will be calculated based

on a pre-specified ranking of outcomes: mortality, cardiac arrest, ECMO, seizures, and dialysis. We will

also explore the inclusion of other clinical endpoints in both the global rank score and composite outcome,

as well as different ranking strategies.

Other secondary exploratory outcomes of general morbidity and end-organ dysfunction will be

measured and compared between the two treatment groups. Please see Table 3 for a description of the

biomarkers and other tests that will be collected or performed.

Other Secondary Exploratory Outcomes:

1. Neurologic:

a. Post-operative intracranial hemorrhage and stroke as measured by Head ultrasound

i. Alternatively, the diagnosis can be made via Head CT or MRI if clinically

indicated by the treatment team

b. Biomarkers for neurologic injury (GFAP, Tau)

c. Incidence of seizures (clinical or sub-clinical by EEG)

2. Respiratory:

a. Mechanical ventilation time (total during hospital stay)

b. Time from surgery to first extubation attempt

c. The T3 Etiometry system will be used to calculate indices of lung compliance (Tidal

volumes, mean airway pressures) on admission, 2, 6, and 24 hours after surgery (or

until extubation)

3. Heart/Circulatory system:

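### The exploratory stroke and haemorrhage outcome pools ultrasound scheduled alike in both arms with discretionary CT/MRI, so recorded rates can differ through unequal imaging (minor)

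*Combined protocol and SAP*

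**What the plan says.** The outcome is item 1.a under Other Secondary Exploratory Outcomes: "Post-operative intracranial hemorrhage and stroke as measured by Head ultrasound". Sub-item i adds "Alternatively, the diagnosis can be made via Head CT or MRI if clinically", and the sentence ends "indicated by the treatment team". A lesion found by either route counts in the same outcome, and the text introducing these outcomes says they will be compared between the two groups.

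The ultrasound route is the same for every infant. The Preoperative section lists "Head ultrasound (not currently standard of care but will be used to evaluate for any brain injury", and the Post-Operative Course section says "A head ultrasound will be performed at 24 and 72 hours after surgery". Table 3 marks the ultrasounds as research tests, pre-operatively and on the mornings of post-operative days 1 and 3, with no distinction by arm.

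On blinding, the Participants section reads "The trial will be unblinded with respect to", then "knowledge of treatment assignment as the majority of clinical personnel will have knowledge of the", then "cardiopulmonary bypass strategy based on blood gases and operative documents".

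The documents give no criteria or time window for CT or MRI, no masked reading or adjudication, no analysis by modality, and no tabulation of CT/MRI use by arm.

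**The concern.** The scheduled ultrasounds give both arms the same opportunity to have a lesion found. The CT/MRI route does not have that protection. Whether an infant is scanned is decided after randomisation, by a team that will mostly know the arm, since ICU staff themselves titrate oxygen to the normoxia targets for the first 24 hours. If CT or MRI shows lesions that ultrasound misses, the arm scanned more often will record more lesions even when true injury is equal.

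Two features of the text add to this. Scheduled ultrasound stops at 72 hours, whereas CT/MRI has no end date, so time at risk of being scanned follows length of stay, which may itself differ by arm. And ultrasound has a pre-operative comparator, whereas CT/MRI has none, so a lesion seen only on CT/MRI cannot be checked like for like as new since surgery.

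What is at stake is the effect size. Aim 3 uses clinical endpoints to inform later trials, and the plan leaves room to explore further endpoints in the composite and the global rank score. Brain injury is a natural question for a strategy that lowers oxygen, and a false signal or false reassurance could be carried forward.

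**Working it through.** The plan states no lesion rate, imaging rate or test accuracy, so it has no figure of its own to reproduce. The only design input is 21 infants per arm (Subject Availability). Everything else below is assumed.

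**Inputs**
- True lesion prevalence p: 20% to 40%, equal in both arms (assumed).
- Ultrasound sensitivity s: 20% to 50% (assumed).
- CT/MRI detects every lesion (assumed).
- Share of infants who have CT/MRI, m: 10% in one arm, 30% in the other (assumed).
- Scanning is independent of lesion status and of the ultrasound result (assumed).

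**Formula.** Recorded rate = p × [s + (1 − s) × m]. The spurious difference is p × (1 − s) × (0.30 − 0.10). Its standard error is √{[r1(1 − r1) + r2(1 − r2)]/21}, where r1 and r2 are the two recorded rates.

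| p | s | Rate, m = 10% | Rate, m = 30% | Difference (points) | Infants of 21 | SE (points) |
|---|---|---|---|---|---|---|
| 20% | 20% | 5.6% | 8.8% | 3.2 | 0.67 | 8.0 |
| 40% | 20% | 11.2% | 17.6% | 6.4 | 1.34 | 10.8 |
| 20% | 50% | 11.0% | 13.0% | 2.0 | 0.42 | 10.0 |
| 40% | 50% | 22.0% | 26.0% | 4.0 | 0.84 | 13.2 |

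The artefact is 2.0 to 6.4 points, or 0.4 to 1.3 infants. One infant is 1/21 = 4.8 points. Relative to its standard error the artefact is about 0.2 (2.0/10.0) to 0.6 (6.4/10.8).

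**Other inputs.** With s of 30% to 50% and CT/MRI sensitivity of 95%, the difference is p × (1 − s) × 0.95 × (gap in m):
- 10% against 30%: 0.20 × 0.50 × 0.95 × 0.20 = 1.9 points, to 0.40 × 0.70 × 0.95 × 0.20 = 5.3 points.
- 10% against 50%: 3.8 to 10.6 points, or 0.8 to 2.2 infants of 21.

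**Checks.** If m is equal in the two arms, or only scheduled ultrasounds count (m = 0), the difference is zero. For scale, Fisher's exact test at 21 per arm needs, for example, 2 against 9 infants for p < 0.05, so an artefact of this size would rarely produce a significant result by itself.

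**Why this is not a bound.** Scans made only to confirm an abnormal ultrasound add no lesion, so the artefact is zero. Scans prompted by signs in infants with a normal ultrasound add more lesions per scan than the formula allows. The true figure could lie on either side of the range.

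**The case against.** The strongest case on the other side has four parts.

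- **The outcome is low-stakes.** It is exploratory, in a 42-infant pilot. It is not the TBARS primary outcome, a listed serious adverse event, or a named component of the global rank score, and no decision rule depends on it. This stands and sets the severity.
- **The imbalance is assumed.** The 10% against 30% gap carries the whole result, and nothing in the documents points to it. A reader might infer that unease about lower oxygen will lead to more scans in the normoxia arm and a false brain-injury signal there. The documents do not support that: they say nothing about scanning by arm, and the opposite direction is as possible. A reader might also infer that everyone who orders a scan knows the arm, but the text says only the majority of clinical personnel. ICU titration makes knowledge likely, not universal.
- **The model is simplified.** Scans must be clinically indicated, so independence from lesion status is not realistic. This stands, which is why the figures are only an illustration.
- **Ultrasound alone would lose information.** On the assumptions above it misses 50% to 80% of lesions. At 20% sensitivity, 4% to 8% would be recorded, about 0.8 to 1.7 infants per arm (21 × 0.04 and 21 × 0.08). MRI-confirmed strokes and lesions after 72 hours would drop out. Accepting a definitive scan is a defensible choice. This stands against replacing the outcome, but not against showing an ultrasound-only comparison beside it.

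None of this removes the mechanism, and no safeguard against it appears elsewhere in the plan.

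**Conclusion.** The point holds as a minor one. The outcome combines a route that is equal by design with a discretionary route that mostly unblinded staff control, so recorded rates can differ through imaging alone. Under the stated assumptions the size is 2.0 to 6.4 points, about 0.4 to 1.3 infants of 21, which is small beside sampling error of 8 to 13 points. It rests on an assumed imaging gap and vanishes if CT/MRI use is equal.

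A reader might go further and conclude that the comparison will be biased, or that CT and MRI findings should not count. The documents support neither. They show an unprotected step, not an actual imbalance, and accepting CT or MRI is a reasonable way to capture lesions more completely.

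**What to change.** Keep the any-modality outcome and add to item 1.a:

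- a between-arm comparison of lesions seen on the scheduled 24-hour and 72-hour ultrasounds, named as the comparison with equal ascertainment;
- by arm, the lesions found only on CT or MRI;
- by arm, the number of infants who had a CT or MRI.

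The cost is a sentence or two and one small table. It needs no new procedure and leaves clinical imaging untouched. The downside is that the ultrasound-only comparison has fewer lesions and misses those seen only on CT/MRI or after 72 hours, but these stay visible in the separate lines. The change equalises the schedule of detection only. It does not make the reading of the ultrasounds masked, on which the plan is silent.

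### Hemorrhage and stroke can be diagnosed on the scheduled ultrasounds or on clinically indicated CT/MRI, so unequal CT/MRI use could shift this exploratory comparison; an ultrasound-only comparison should be reported beside it

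*Combined protocol and SAP*

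**What the plan says.** Under Other Secondary Exploratory Outcomes, 1. Neurologic, item a is "Post-operative intracranial hemorrhage and stroke as measured by Head ultrasound". Its sub-item adds a second route to the same diagnosis: "Alternatively, the diagnosis can be made via Head CT or MRI if clinically", continuing "indicated by the treatment team". The outcomes in this list are to be compared between the two arms.

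The ultrasound route is uniform. Study Protocol, 1. Preoperative, gives each enrolled infant a baseline ultrasound, described as "not currently standard of care but will be used to evaluate for any brain injury" in each group. Under 5. Post-Operative Course, "A head ultrasound will be performed at 24 and 72 hours after surgery". Table 3 lists these scans as research tests (pre-op, POD 1 and POD 3) with no distinction by arm.

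The CT/MRI route is discretionary. Neither scan appears in Table 3. The documents give no ordering criteria, no time limit for a post-operative lesion, no reader blinded to arm, no rule for disagreement between modalities, no ultrasound-only comparison and no report of how many infants were scanned.

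On blinding, Study Design, Participants, states "The trial will be unblinded with respect to" "knowledge of treatment assignment as the majority of clinical personnel will have knowledge of the" bypass strategy, from blood gases and operative records.

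**The concern.** Ascertainment has two parts. One is the same for every infant; the other depends on a clinical decision, usually made by people who know the arm. A lesion seen on either scheduled ultrasound is counted whatever else is ordered. A lesion that both ultrasounds miss, or that appears after 72 h, is counted only if someone requests CT or MRI.

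If CT/MRI is used at different rates in the two arms, the recorded rates of hemorrhage and stroke can differ with identical underlying injury. The comparison then mixes injury with frequency of imaging, and the planned reporting would not let a reader separate them. At 21 infants per arm, one event more or less can change the apparent direction of a difference, and the pilot is meant to inform a larger trial.

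**Working it through.** The plan states no lesion rate, imaging rate or sensitivity for this outcome, so it has no figure to reproduce. The first step is textual; the second is an illustration of size.

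**Which lesions are affected**

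| Lesion | Infant not sent for CT/MRI | Infant sent for CT/MRI |
|---|---|---|
| Seen on the 24 or 72 h ultrasound | counted | counted |
| Missed by both ultrasounds | not counted | counted if the scan shows it |
| Arises after 72 h | not counted | counted if the scan shows it |

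Only the last two rows can be distorted. A related case is a lesion present before surgery but invisible on the baseline ultrasound. First seen on a post-operative CT or MRI, it could be recorded as post-operative, again only in infants who are scanned.

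**Illustration of size**

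From the documents: 21 infants per arm. Everything else is assumed:
- p, the true lesion rate, equal in both arms;
- s, the sensitivity of the two ultrasounds together;
- CT/MRI sensitivity, 0.95;
- m, the proportion of infants given CT/MRI in an arm.

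The sub-item is read as allowing either route to make the diagnosis, and scanning is taken as independent of lesion status and ultrasound result.

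Recorded rate = p × [s + (1 − s) × 0.95 × m]

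Spurious difference = p × (1 − s) × 0.95 × (m₂ − m₁)

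With p = 0.30 and a 20-point gap in scanning, the difference is 0.30 × 0.95 × 0.20 × (1 − s) = 0.057 × (1 − s):

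| s | Difference | Events per 21 | Ratio, 10% v 30% scanned | Ratio, 20% v 40% scanned |
|---|---|---|---|---|
| 0.20 | 4.6 points | 1.0 | 1.55 | 1.43 |
| 0.40 | 3.4 points | 0.7 | 1.25 | 1.22 |
| 0.60 | 2.3 points | 0.5 | 1.12 | 1.11 |

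For example, at s = 0.20 and 10% v 30% scanned, the recorded rates are 0.30 × (0.20 + 0.80 × 0.095) = 8.3% and 0.30 × (0.20 + 0.80 × 0.285) = 12.8%.

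A wider range, p = 0.10-0.40 and s = 0.30-0.70:
- 10% v 30% scanned: 0.6 to 5.3 points, or 0.1 to 1.1 infants of 21.
- 10% v 50% scanned: 1.1 to 10.6 points, or 0.2 to 2.2 infants of 21.

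At 10% v 50%, the chance of Fisher p ≤ 0.05 with no true difference, by exact enumeration, is 2.6% at p = 0.20, s = 0.50. It is 7.8% at p = 0.40, s = 0.30, against 2.1% for those same rates with 10% scanned in both arms. A misleading count is thus more likely than a misleading significant test.

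**Checks on the mechanism**

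If m is equal in both arms, the difference is zero. If the outcome is scored from the scheduled ultrasounds alone, the recorded rate is p × s in each arm, and CT/MRI ordering cannot alter the comparison. That requires complete scheduled scans and equal reading in both arms.

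**The case against.** The strongest reply is that the stakes are low and unequal scanning is unproven. Hemorrhage and stroke are one item in an exploratory list. They are not the TBARS primary outcome, a listed serious adverse event or one of the five pre-specified rank-score components. GFAP and Tau give scheduled neurologic measures in both arms. This stands, and it sets the severity. The one qualification is that the plan also intends to explore adding other clinical endpoints to the composite and rank score.

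A second reply is that an ultrasound-only count discards real events. At the assumed sensitivity of 20-60%, it would miss 40-80% of lesions, including any stroke shown only on CT or MRI. This also stands: which count should lead is a trade-off between bias and completeness. It argues for showing both, not for showing only the any-modality count.

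A third reply concerns the model. If CT or MRI is often ordered to follow up an abnormal ultrasound, it adds fewer new events than calculated. The documents do not say how often that happens.

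A reader might also infer that normoxia infants would be scanned more, because the written instruction to verify oxygen delivery by NIRS, mixed venous saturation and lactate appears only for that arm. The documents do not support this. The instruction belongs to weaning from bypass and does not concern neurologic work-up. NIRS and blood gases with lactate are standard of care for all infants in Table 3, and the circulatory outcomes describe them as routine.

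**Conclusion.** The point holds as a minor one. The definition leaves this comparison open to differential ascertainment, and nothing elsewhere in the documents closes the gap. Under the assumed rates and a 20-point gap in scanning, the shift is about 0.5 to 1 event per 21 infants. It reaches about 2 only at the extreme of a 40-point gap, and it is zero if scanning is equal. Every rate behind these figures is an assumption.

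Three stronger conclusions are tempting and should not be drawn:
- That the arms will differ through imaging, or that normoxia will look worse. Knowledge of the arm makes unequal ordering possible, but its direction is unknown.
- That every CT or MRI counts at any time. The text requires a clinical indication; what it lacks is a definition of that indication and a time window.
- That the brain is the organ of greatest concern under lower oxygen. The documents do not say so. The Background reports lower brain-injury biomarkers with lower oxygen levels, and Hypothesis 1b expects reduced neurologic injury.

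**What to change.** Add a sentence to item 1a requiring two between-arm comparisons side by side: hemorrhage or stroke on the scheduled 24 and 72 h ultrasounds alone, and on any modality. List CT/MRI-only diagnoses separately, with the number of infants scanned per arm, the indication and the timing. State that a difference seen only in the any-modality count may reflect imaging frequency. Reading the ultrasounds blind to arm and stating a time window for the any-modality count would strengthen this further, but the main repair does not depend on them.

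The cost is that sentence and a small table. The ultrasounds are already scheduled, and CT/MRI results arise from care. The downside is that the ultrasound-only count misses lesions seen only on CT or MRI; these remain visible in the other lines. No change to clinical imaging is proposed.
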